5.3 Exclusion criteria

Patients eligible for this study must not meet any of the following criteria:

1. Patients who have therapies available that are known to confer a clinical benefit will be excluded from the study.
2. Neurological symptoms related to underlying disease requiring increasing doses of corticosteroids. Note: Steroid use for management of CNS tumors is allowed but must be at a stable dose for at least 2 weeks preceding study entry.
3. History of another primary malignancy except adequately treated *in situ* carcinoma of the cervix or non-melanoma carcinoma of the skin or any other curatively treated malignancy that is not expected to require treatment for recurrence during the course of the study or affect survival.
4. Any other medical condition that would, in the investigator's judgment, prevent the patient's participation in the clinical study due to safety concerns or compliance with clinical study procedures.
5. Current evidence of corneal or retinal disorder/keratopathy including, but not limited to, bullous/band keratopathy, corneal abrasion, inflammation/ulceration, keratoconjunctivitis, confirmed by ophthalmologic examination.
6. History and/or current evidence of extensive tissue calcification including, but not limited to, the soft tissue, kidneys, intestine, myocardium and lung with the exception of calcified lymph nodes, minor pulmonary parenchymal calcifications, and asymptomatic coronary calcification.
7. Impairment of gastrointestinal (GI) function or GI disease that may significantly alter the absorption of oral Infigratinib (e.g., ulcerative diseases, uncontrolled nausea, vomiting, diarrhea, malabsorption syndrome, small bowel resection).
8. Current evidence of endocrine alterations of calcium/phosphate homeostasis, e.g., parathyroid disorders, history of parathyroidectomy, tumor lysis, tumoral calcinosis etc.
9. Treatment with any of the following anti-cancer therapies prior to the first dose of Infigratinib within the stated timeframes:
 - a. Cyclical chemotherapy (intravenous) within a period of time that is shorter than the cycle length used for that treatment (e.g., 6 weeks for nitrosourea, mitomycin-C)
 - b. Biological therapy (e.g., antibodies – including bevacizumab) within a period of time that is \leq 5 t1/2 or \leq 4 weeks, whichever is shorter, prior to starting study drug
 - c. Continuous or intermittent small molecule therapeutics within a period of time that is \leq 5 t1/2 or \leq 4 weeks (whichever is shorter) prior to starting study drug
 - d. Any other investigational agents within a period of time that is \leq 5 t1/2 or less than the cycle length used for that treatment or \leq 4 weeks (whichever is shortest) prior to starting study drug
 - e. Wide field radiotherapy (including therapeutic radioisotopes such as strontium 89) \leq 4 weeks or limited field radiation for palliation \leq 2 weeks prior to starting study drug
10. Patients who are currently receiving treatment with agents that are known strong inducers or inhibitors of CYP3A4 and medications which increase serum phosphorus and/or calcium concentration are excluded. (Refer to Appendix 2 for list of prohibited medications). Patients are not permitted to receive enzyme-inducing anti-epileptic drugs.
11. Consumption of grapefruit, grapefruit juice, grapefruit hybrids, pomegranates, star fruits, pomelos, Seville oranges or products within 7 days prior to first dose.
12. Use of medications that are known to prolong the QT interval and/or are associated with a risk of Torsades de Pointes (TdP) 7 days prior to first dose.
13. Use of amiodarone within 90 days prior to first dose.
14. Current use of therapeutic doses of warfarin sodium or any other coumadin-derivative anticoagulants. Heparin and/or low molecular weight heparins are allowed.

15. Insufficient bone marrow function:
 - a. ANC \leq 1,000/mm³ [$1.0 \times 10^9/L$]
 - b. Platelets \leq 75,000/mm³ [$75 \times 10^9/L$]
 - c. Hemoglobin \leq 9.0 g/dL
16. Insufficient hepatic and renal function:
 - a. Total bilirubin \geq 1.5x ULN unless associated with patient's primary cancer and/or metastases and with Principal Investigator's approval
 - b. AST and ALT \geq 3x ULN unless associated with patient's primary cancer and/or metastases and with Principal Investigator's approval
 - c. Alkaline phosphatase \geq 2.5x ULN unless associated with patient's primary cancer and/or metastases and with Principal Investigator's approval
 - d. Calculated or measured creatinine clearance of < 40 mL/min
17. Calcium-phosphate homeostasis:
 - a. Inorganic phosphorus outside of institutional normal limits
 - b. Total serum calcium (can be corrected) outside of institutional normal limits
18. Clinically significant cardiac disease including any of the following:
 - a. Congestive heart failure requiring treatment (NYHA Grade \geq 2), LVEF $< 50\%$ as determined by MUGA scan or ECHO, or uncontrolled hypertension (refer to WHOISH guidelines)
 - b. History or presence of clinically significant ventricular arrhythmias, atrial fibrillation, resting bradycardia, or conduction abnormality
 - c. Unstable angina pectoris or acute myocardial infarction \leq 3 months prior to starting study drug
 - d. QTcF > 470 msec (males and females)
 - e. History of congenital long QT syndrome
19. Pregnant or nursing (lactating) women, where pregnancy is defined as the state of a female after conception and until the termination of gestation, confirmed by a positive hCG laboratory test.
20. Women of child-bearing potential (WOCBP), defined as all women physiologically capable of becoming pregnant, unless they are using highly effective methods of contraception during dosing and for 3 months following the discontinuation of study treatment. Highly effective contraception methods include:
 - a. Total abstinence (when this is in line with the preferred and usual lifestyle of the patient. Periodic abstinence (e.g., calendar, ovulation, symptothermal, post-ovulation methods) and withdrawal are not acceptable methods of contraception.
 - b. Female sterilization (have had surgical bilateral oophorectomy with or without hysterectomy) or tubal ligation at least six weeks before taking study treatment. In case of oophorectomy alone, only when the reproductive status of the woman has been confirmed by follow-up hormone level assessment.
 - c. Male sterilization (at least 6 months prior to screening). For female patients on the study the vasectomized male partner should be the sole partner for that patient.
 - d. Use of oral, injected or implanted hormonal methods of contraception or placement of an intrauterine device (IUD) or intrauterine systems (IUS), or other forms of hormonal contraception that have comparable efficacy (failure rate $< 1\%$), for example hormone vaginal ring or transdermal hormone contraception.

In case of use of oral contraception women should have been stable on the same pill for a minimum of 3 months before taking study treatment.

Women are considered post-menopausal and not of child bearing potential if they have had 12 months of natural (spontaneous) amenorrhea with an appropriate clinical profile (e.g. age appropriate, history of vasomotor symptoms) or have had surgical bilateral oophorectomy (with or without hysterectomy) or tubal ligation at least 6 weeks ago. In the case of oophorectomy alone, only when the reproductive status of the woman has been confirmed by follow-up hormone level assessment is she considered not of child bearing potential.

21. Sexually active males unless they use a condom during intercourse while taking drug and for 3 months after the last dose of the study drug and should not father a child in this period. A condom is required to be used also by vasectomized men as well as during intercourse with a male partner in order to prevent delivery of the drug via seminal fluid.

6. Treatment

The investigational drug will be Infigratinib as an oral formulation.

6.1 Study treatment

The pharmacist will dispense the correct number and dose strength of capsules to ensure that each patient receives sufficient drug until the next scheduled visit.

6.1.1 Dosing regimen

Table 4: Dose and treatment schedule

Study treatment	Formulation	Pharmaceutical form and route of administration	Dose	Frequency and/or Regimen
Infigratinib	FMIv3	Capsule(s) for oral use	125 mg (administered as one 100 mg capsule and one 25 mg capsule)	Daily (3 weeks on, 1 week off schedule in 28-day cycles)

6.1.1.1 Instructions for administration of Infigratinib

- Patients should be instructed to take the daily dose of Infigratinib in the morning, at approximately the same time each day (24 ± 2 hour interval).
- Infigratinib should be administered in the fasted state at least 1 hour before or 2 hours after a meal.
- Infigratinib should be taken with a large glass of water (~250 mL) and consumed over as short a time as possible. Patients should be instructed to swallow the capsules whole and not chew them.
- If the patient forgets to take the scheduled dose in the morning, he/she should not take the dose more than 2 hours after the usual time and should continue treatment the next day. Any doses that are missed should be skipped altogether and should not be replaced or made up at the next scheduled dosing.
- If vomiting occurs following the dosing of study drug, re-dosing is not permitted that same day. Dosing should resume the next day.
- Infigratinib is characterized by pH-dependent solubility, and therefore, medicinal products that alter the pH of the upper gastro-intestinal tract may alter the solubility of Infigratinib, and limit

bioavailability. These agents include, but are not limited to, proton pump inhibitors (e.g., omeprazole), H2-antagonists (e.g., ranitidine) and antacids. Therefore, Infigratinib should be dosed at least 2 hours before or 10 hours after dosing with a gastric protection agent.

- Patients must avoid consuming grapefruits, grapefruit juice, grapefruit hybrids, pomegranates, star fruits, pomelos, Seville oranges or juice within 7 days prior to the first dose of study medication, through the end of study participation. This is due to a potential CYP3A4 interaction with study medication. Normal oranges and orange juice are allowed.
- The investigator or responsible site personnel should instruct the patient to take the study drug exactly as prescribed to promote compliance. All dosages prescribed and dispensed to the patient and all dose changes or missed doses during the study must be recorded on the Dosage Administration Record eCRF.
- Drug accountability must be performed on a regular basis. Patients will be instructed to return unused study drug to the site at the end of each cycle. The site personnel will ensure that the appropriate dose of each study drug is administered at each visit and will provide the patient with the correct amount of drug for subsequent dosing.
- Patients will be given a drug diary to complete with each cycle.

6.1.2 Ancillary treatments

Phosphate-lowering treatment, including low phosphate diet and phosphate binding therapy such as sevelamer hydrochloride, should be implemented prophylactically with meals on the first day of study drug initiation and modified as clinically indicated throughout Infigratinib administration. Recommendations for treatment are provided in **Table 6**, but should be modified as per country or institutional guidelines.

6.1.3 Treatment duration

All patients will receive Infigratinib daily on a three week on (21 days), one week off (7 days) schedule in 28-day cycles. Patients may continue treatment with Infigratinib until the patient experiences unacceptable toxicity, disease progression, treatment is discontinued at the discretion of investigator or withdrawal of consent, or death.

6.2 Dose modifications

6.2.1 Dose modifications and dose delay

For patients who do not tolerate the protocol-specified dosing schedule, dose adjustments are permitted in order to allow the patient to continue the study treatment. All dose modifications should be based on the worst preceding toxicity (**Table 6**). Dosage changes must be recorded on the Dosage Administration Record CRF.

The following guidelines should be applied.

Each patient will be allowed 3 dose reductions. Patients should discontinue Infigratinib if toxicities persist following 3 dose reductions (**Table 5**).

Following resolution of toxicity to baseline or \leq Grade 1, treatment is resumed at either the same or lower dose of study drug as per the criteria in **Table 6**. If treatment is resumed at the same dose of study drug, and the same toxicity recurs with the same or worse severity regardless of duration, dose must be reduced to the next lower dose level. If treatment is resumed at the lower dose of study drug, and the same toxicity recurs with the same or worse severity, the patient should have a second dose reduction.

Patients who discontinue the study for a study related adverse event or an abnormal laboratory value must be followed as described in Section 8.

In exceptional situations, study treatment may continue even if the patient experienced one of the treatment stopping rules. The decision to allow for continuation of treatment will be made on a case-by-case basis following discussion with the Principal Investigator (Sponsor).

Situations that may allow for continuation of treatment include the following:

- A dose delay of > 14 days has occurred, but the patient is clearly benefiting from study treatment (i.e., stable disease, partial response, or complete response) and it is the investigator's opinion that no safety concerns are present. If the patient is clearly benefiting from the study treatment (i.e. stable disease, partial response, or complete response), and in the opinion of the investigator no safety concerns are present, after discussion with QED Therapeutics Medical Monitor, the patient may remain on the study treatment.
- A third or subsequent reduction (to 50 mg) in dose may be allowed if the patient is clearly benefiting from study treatment (i.e., stable disease, partial response, or complete response) but is experiencing adverse events that prevent continued treatment at the already reduced dose.

Table 5: Dose reduction table

Dose reduction				
	Starting dose level 0	Dose level -1	Dose level -2	Dose level -3
Infigratinib	125 mg	100 mg	75 mg	50 mg

Table 6: Criteria for interruption and re-initiation of Infigratinib treatment

Worst Toxicity CTCAE v5.0 Grade (unless otherwise specified)	Recommended Dose Modifications any time during a cycle of therapy
Cardiac disorders	

Worst Toxicity CTCAE v5.0 Grade (unless otherwise specified)	Recommended Dose Modifications any time during a cycle of therapy
Cardiac - Prolonged QTcF interval Grade 1 and 2: QTcF \geq 481msec and \leq 500 msec (asymptomatic)	Maintain dose level of Infigratinib ECG (Electrocardiogram) assessments should be performed for 2 additional cycles at the same frequency as in cycle 1, or as clinically indicated 
 • If ECG assessments show no QTcF \geq 481 msec, for subsequent cycles ECG monitoring will be performed as per visit schedule. • If ECG assessments are still abnormal (QTcF \geq 481 msec and \leq 500 msec), then ECG monitoring must continue at the same frequency as in cycle 1 for all subsequent cycles.
Grade 3: QTcF $>$ 500msec as identified on the ECG by the investigator	
 • Hold Infigratinib. • Monitor patient with hourly ECGs until the QTcF has returned to baseline. • Perform further monitoring as clinically indicated. • Exclude other causes of QTcF prolongation such as hypokalemia, hypomagnesaemia and decreased blood oxygenation. • Patients should receive appropriate electrolyte replacement and should not receive further Infigratinib until electrolytes are documented to be within normal limits. 
Once the QTcF prolongation has resolved and if the QTcF prolongation was confirmed by the central reader, patients may be re-treated at one lower dose level at the investigator's discretion
 
 • ECG assessments should be performed for 2 additional cycles at the same frequency as in cycle 1 or as clinically indicated 
 ◦ If ECG assessments show no QTcF \geq 481 msec, for subsequent cycles ECG monitoring will be performed as per visit schedule. ◦ If ECG assessments are still abnormal (QTcF \geq 481 msec and \leq 500 msec), then ECG monitoring must continue at the same frequency as in cycle 1 or as clinically indicated, for all subsequent cycles • Patients who experience recurrent QTcF \geq 500msec after one dose reduction will be discontinued from study. 
NB: If ventricular arrhythmia or Torsades de Pointes is observed in a patient, he/she will be discontinued from the study.
 
Whenever QTcF $>$ 500msec is observed, a plasma sample for determination of Infigratinib concentration

Worst Toxicity CTCAE v5.0 Grade (unless otherwise specified)	Recommended Dose Modifications any time during a cycle of therapy
	should be obtained with the time of sample collection noted.
Cardiac disorders - others Grade \geq 3, or congestive heart failure \geq 2	Discontinue patient from study treatment.
Investigations-Hematology	
ANC decreased (Neutropenia) Grade 3 (ANC $< 1.0 - 0.5 \times 10^9/L$)	Hold dose of Infigratinib until resolved to CTCAE Grade \leq 1 or baseline, then: 
 • If resolved within \leq 7 days, maintain dose level of Infigratinib • If resolved within $>$ 7 days, \downarrow 1 dose level of Infigratinib. Grade 4 (ANC $< 0.5 \times 10^9/L$)
Febrile neutropenia Grade 3 (ANC $< 1.0 \times 10^9/L$, single temperature of $> 38.3^{\circ}C$ or 101F, or a sustained temperature of $\geq 38.0^{\circ}C$, or 100.4F)	Hold dose of Infigratinib until resolved to CTCAE Grade \leq 1, then: 
 • If resolved within \leq 7 days, \downarrow 1 dose level of Infigratinib. • If not resolved within 7 days discontinue patient from study drug treatment. Grade 4
Hemoglobin Grade 3 (<8.0 mg/dL, transfusion indicated)	Hold dose of Infigratinib until resolved or corrected to CTCAE Grade \leq 1 or baseline, then maintain dose level
	Grade 4 (Life-threatening consequences; urgent intervention indicated)
	Hold dose of Infigratinib until resolved or corrected to CTCAE Grade \leq 1 or baseline, then \downarrow 1 dose level

Worst Toxicity CTCAE v5.0 Grade (unless otherwise specified)	Recommended Dose Modifications any time during a cycle of therapy
Platelet count decreased (Thrombocytopenia)	
Grade 3 (PLT < 50 - 25 x 10 ⁹ /L) without bleeding	
Hold dose of Infigratinib until resolved to CTCAE Grade ≤ 1 or baseline
 
 • If resolved within ≤ 7 days, maintain dose level of Infigratinib. • If resolved within > 7 days, ↓ 1 dose level of Infigratinib
Grade 3 (PLT < 50 - 25 x 10 ⁹ /L) with bleeding or Grade 4 (PLT < 25 x 10 ⁹ /L)	Hold dose of Infigratinib until resolved to CTCAE Grade ≤ 1 or baseline, then ↓ 1 dose level
Investigations – Renal	
Serum creatinine ≥ Grade 2	
Grade 2 (> 1.5 - 3.0 x ULN or baseline)	
If serum creatinine CTCAE Grade ≥ 2 has been demonstrated in conjunction with hyperphosphatemia, serum creatinine levels must be repeated at least weekly until resolution. 24-hour urine collection should be obtained as clinically indicated for total phosphate, calcium, protein, and creatinine clearance. Ultrasound examination of the kidneys should be performed as indicated to evaluate de-novo calcifications until resolution or stabilization of creatinine.

Grade ≥ 3 (> 3.0 x baseline; >3.0-6.0 x ULN)	
Hold dose of Infigratinib until resolved to Grade ≤1 or baseline:
 
 • If resolved within ≤ 7 days, maintain dose level of Infigratinib. • If resolved within > 7 days, ↓ 1 dose level of Infigratinib.
Grade ≥ 3 (> 3.0 x baseline; >3.0-6.0 x ULN)	
Discontinue patient from study treatment.	
Investigations – Hepatic	

Worst Toxicity CTCAE v5.0 Grade (unless otherwise specified)	Recommended Dose Modifications any time during a cycle of therapy

Blood bilirubin (patients with Gilbert Syndrome these dose modifications apply to changes in direct bilirubin only)
 
Grade 2 ($>1.5 - 3.0 \times \text{ULN}$ if baseline was normal; $>1.5-3.0 \times \text{baseline}$ if baseline was abnormal)
 
Grade ≥ 3 ($> 3.0 - 10.0 \times \text{ULN}$ if baseline was normal; $>3.0 - 10.0 \times \text{baseline}$ if baseline was abnormal)
	
Hold dose of Infigratinib until resolved to CTCAE Grade ≤ 1
 
 • If resolved within ≤ 7 days, maintain dose level of Infigratinib. • If resolved within > 7 days, $\downarrow 1$ dose level of Infigratinib. 
Discontinue patient from study treatment.
 
Note: If CTCAE Grade 3 or 4 hyperbilirubinemia is due to hemolysis, then $\downarrow 1$ dose level of Infigratinib and continue treatment at the discretion of the Investigator.

AST or ALT
 
Grade 3 ($> 5.0 - 20.0 \times \text{ULN}$ if baseline was normal; $>5.0 - 20.0 \times \text{baseline}$ if baseline was abnormal) without bilirubin elevation $> 2.0 \times \text{ULN}$
 
Grade 4 ($> 20.0 \times \text{ULN}$ if baseline was normal; $>20.0 \times \text{baseline}$ if baseline was abnormal) without bilirubin elevation $>2.0 \times \text{ULN}$
	
Hold dose of Infigratinib until resolved to CTCAE Grade ≤ 1 or baseline
 
 • If resolved within ≤ 7 days, maintain dose level of Infigratinib. • If resolved within > 7 days, $\downarrow 1$ dose level of Infigratinib. 
Discontinue patient from study treatment.

AST or ALT and Bilirubin
 
AST or ALT $> 3.0 - 5.0 \times \text{ULN}$ and total bilirubin $> 2.0 \times \text{ULN}$ without liver metastasis or evidence of disease progression in the liver
 
AST or ALT $> 5.0 \times \text{ULN}$ and total bilirubin $> 2.0 \times \text{ULN}$; no evidence of biliary obstruction or other causes that can reasonably explain the concurrent elevation
	
Hold dose of Infigratinib until resolved to CTCAE Grade ≤ 1
 
 • If resolved within ≤ 7 days, $\downarrow 1$ dose level of Infigratinib. • If resolved within > 7 days, discontinue patient from study treatment. 
Discontinue patient from study treatment.

Worst Toxicity CTCAE v5.0 Grade (unless otherwise specified)	Recommended Dose Modifications any time during a cycle of therapy
Laboratory / Metabolic disorders	
Asymptomatic amylase and/or lipase elevation	
Grade 3 (> 2.0 - 5.0 x ULN with signs or symptoms; >5.0 x ULN and asymptomatic)
 
 • Hold dose of Infigratinib until resolved to CTCAE Grade \leq 2. • ↓ 1 dose level of Infigratinib 
For recurrent Grade 3 asymptomatic lipase or amylase elevation despite dose reduction, drug should be held and continuation of therapy should be discussed with the medical monitor following resolution to \leq Grade 2.

Grade 4 (>5.0 x ULN and with signs and symptoms)	
For any Grade 4 asymptomatic lipase or amylase elevation, drug should be held and continuation of therapy should be discussed with the medical monitor following resolution to \leq Grade 2.

	
Note: A CT scan or other imaging study to assess the pancreas, liver, and gallbladder should be performed as clinically indicated within 1 week of the first occurrence of any CTCAE \geq Grade 3 amylase and/or lipase.

Hyperphosphatemia	
Grade 1: Laboratory finding only and intervention not indicated	
Maintain dose level of Infigratinib and optimize phosphate lowering therapy as clinically indicated.

Grade 2: Noninvasive intervention indicated	
Maintain dose level of Infigratinib and optimize phosphate lowering therapy as clinically indicated.

Grade 3: Severe or medically significant but not immediately life-threatening; hospitalization or prolongation of existing hospitalization indicated	
Hold Infigratinib until resolved \leq Grade 2. Restart at same dose level with maximal phosphate binder dosing.

Grade 4: Life-threatening consequences; urgent intervention indicated (e.g. dialysis)	
Hold Infigratinib until resolved \leq Grade 2. Reduce one dose level dose level with maximal phosphate binder dosing.

	
It is recommended that phosphate binder dosing continues during Infigratinib dose interruptions for hyperphosphatemia and that serum phosphorus values be monitored frequently, e.g. every 2-3 days.

	
Phosphate binder dosing should be held during the week off Infigratinib therapy each cycle (Days 22-28) and during Infigratinib dose interruptions for non-hyperphosphatemia adverse events.

Worst Toxicity CTCAE v5.0 Grade (unless otherwise specified)	Recommended Dose Modifications any time during a cycle of therapy
Hypercalcemia Serum calcium Grade 2 or 3	Hold Infigratinib dose until resolved to Grade 1 or baseline: 
 if resolved within \leq 7 days after suspending Infigratinib, maintain dose level if resolved within $>$ 7 days after suspending Infigratinib, \downarrow 1 dose level
Serum calcium \geq Grade 4	Discontinue patient from the study
Nervous system disorders	
Neurotoxicity Grade 2	Omit dose of Infigratinib until resolved to CTCAE Grade \leq 1, then \downarrow 1 dose level of Infigratinib
Grade \geq 3	Discontinue patient from study drug treatment
GI disorders	
Pancreatitis Grade 2 (Enzyme elevation; radiologic findings only)	Hold Infigratinib dose until resolved to Grade 1 or baseline: 
 if resolved within \leq 7 days after suspending Infigratinib, maintain dose level if resolved within $>$ 7 days after suspending Infigratinib, \downarrow 1 dose level
Grade \geq 3 (Severe pain; vomiting; medical intervention indicated)	Discontinue patient from study drug treatment
Diarrhea Grade 1	Maintain dose level of Infigratinib, initiate anti-diarrheal treatment
Grade 2	
 Hold dose of Infigratinib until resolved to CTCAE Grade \leq 1 Optimize anti-diarrheal treatment, maintain dose level of Infigratinib. For reoccurrence of diarrhea CTCAE Grade 2, hold dose of Infigratinib until resolved to CTCAE Grade \leq 1, \downarrow Infigratinib by 1 dose level

Worst Toxicity CTCAE v5.0 Grade (unless otherwise specified)	Recommended Dose Modifications any time during a cycle of therapy
Grade 3	
 • Hold dose of Infigratinib until resolved to CTCAE Grade \leq 1 • Optimize anti-diarrheal treatment • \downarrow Infigratinib by 1 dose level • For reoccurrence of diarrhea CTCAE Grade 3, despite optimal antidiarrheal treatment, discontinue patient from study treatment.
Grade 4	
Discontinue patient from study treatment.
 
Note: Antidiarrheal medication is recommended at the first sign of abdominal cramping, loose stools or overt diarrhea

Vomiting Grade 2 not controlled by optimal anti-emetic therapy Grade 3 not controlled by optimal anti-emetic therapy or Grade 4	Hold Infigratinib doses until \leq Grade 1, \downarrow 1 dose level Discontinue patient from study
Eye Disorders (confirmed by ophthalmologic examination)	
Retinal disorders Grade 2 central serous retinopathy and central serous retinopathy -like events Grade 3 central serous retinopathy and central serous retinopathy-like events and any other Grade 3 eye disorders \geq Grade 1 retinal vein occlusion, Grade 4 central serous retinopathy and central serous retinopathy-like events, and Grade 4 other eye disorders	Hold Infigratinib until resolved to \leq Grade 1 and continue ophthalmologic evaluation 
 • If resolved within \leq 14 days, \downarrow Infigratinib by 1 dose level • If resolved within $>$ 14 days, discontinue Infigratinib Hold Infigratinib until resolved to Grade \leq 1. 
 • If resolved within \leq 14 days, \downarrow Infigratinib by 1 dose level • If resolved within $>$ 14 days, discontinue Infigratinib Discontinue Infigratinib
Other ocular/visual toxicity \geq Grade 3	Hold Infigratinib until resolution to \leq Grade 1 If resolution within \leq 14 days, \downarrow 1 dose level, otherwise discontinue Infigratinib
General disorders	

Worst Toxicity CTCAE v5.0 Grade (unless otherwise specified)	Recommended Dose Modifications any time during a cycle of therapy
Fatigue Grade 3	Hold dose of Infigratinib until resolved to CTCAE Grade ≤ 1. If resolved within ≤ 7 days, maintain dose level of Infigratinib.
Other clinically significant AEs	
Grade 3	Hold dose of Infigratinib until resolved to CTCAE Grade ≤ 1, then ↓ 1 dose level of Infigratinib.
Grade 4	Discontinue patient from study treatment.
All dose modifications should be based on the worst preceding toxicity. Once a dose reduction has occurred dose re-escalation may be allowed on a case by case basis after discussion with the Principal Investigator/Sponsor. Patients who require more than two dose reductions of Infigratinib will be generally discontinued from study drug treatment.	

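### Section 6.2.1 gives a second dose reduction for a toxicity that recurs at a reduced dose, two Table 6 rows order discontinuation for the same event, and the protocol does not say which governs

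*Combined protocol and SAP*

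**What the plan says.** Section 6.2.1 covers resumption after a toxicity has resolved. Its rule for a recurrence at a reduced dose has a condition, "If treatment is resumed at the lower dose of study drug", and a consequence: if "the same toxicity recurs with the same or worse severity, the patient should have a second dose reduction". No toxicity is exempted.

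Table 6, in the same section, has its own recurrence instructions for some toxicities:

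- **Grade 3 diarrhea.** The first event leads to a hold and a reduction of one level. Then: "For reoccurrence of diarrhea CTCAE Grade 3, despite optimal antidiarrheal treatment, discontinue patient from study treatment".
- **QTcF above 500 msec.** The first event leads to a hold. After resolution and confirmation by the central reader, "patients may be re-treated at one lower dose level" at the investigator's discretion. For a recurrence, the row says that patients with QTcF at or above "500msec after one dose reduction will be discontinued from study".

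The text and the table are linked by a general cross-reference, "All dose modifications should be based on the worst preceding toxicity", and by a pointer to Table 6 for the choice between the same and a lower dose at resumption. Section 6.2.1 also lets treatment continue past a stopping rule in exceptional cases, after discussion with the Principal Investigator.

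**The concern.** In both rows the patient is already on a reduced dose when the toxicity returns, which is exactly the condition of the general rule. Read literally, Section 6.2.1 keeps the patient on drug at a second reduction, while Table 6 takes the patient off. One of the two events is QTcF prolongation above 500 msec, where the action should not be open to interpretation.

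The trial is multi-center, so two sites could resolve the same event differently. Several planned summaries would record that difference:

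- the tolerability endpoints of interruptions, reductions and dose intensity (Section 3.2);
- adverse events leading to delay or discontinuation (Section 7.2.2);
- study-drug compliance, measured by reductions and interruptions (Section 10.3);
- the tabulation of events that end treatment (Section 10.5).

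Section 12 allows no authorized deviations. A site that follows one text departs from the other, and a deviation classed as major removes the patient from the Per-Protocol Set (Section 10.2).

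**Working it through.** The plan gives no figure to reproduce on this point. The check sets the rules side by side and then bounds the number of patients.

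**Step 1: do both rules apply to the same event?**

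| Event at a reduced dose | Section 6.2.1 | Table 6 | Same trigger? |
|---|---|---|---|
| Grade 3 diarrhea recurs although antidiarrheal treatment is optimised | Second reduction | Discontinue study treatment | Yes. The row itself imposes the first reduction. |
| QTcF recurs after one reduction | Second reduction | Discontinue from study | Yes, for values above 500 msec. |

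The QTcF overlap needs one refinement. Table 6 puts values from 481 to 500 msec in its Grade 1-2 row. A recurrence at exactly 500 msec is therefore less severe than the first event, and the general rule, which needs the same or worse severity, does not reach it. Above 500 msec both rules apply and disagree.

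**Step 2: is there a precedence clause?** Three pieces of text could supply one.

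- The cross-reference to the worst preceding toxicity sets the basis for a modification. It does not rank the text against the table.
- The pointer to Table 6 for the resumption dose is attached to the first resumption. The two recurrence sentences that follow it carry no such pointer.
- The exceptional-continuation clause allows case-by-case departures from stopping rules. It does not say which recurrence rule is the stopping rule.

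None states an order of precedence.

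**Step 3: does the table always depart from the text?** No. For Grade 2 diarrhea the first event is handled at an unchanged dose and a recurrence brings a reduction of one level. That agrees with the general rule for a recurrence after resumption at the same dose. Table 6 thus follows the general rules in one place and departs from them in others, without marking the departures.

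**Step 4: how many patients?** Inputs are from Section 1.2.1.4.1, which reports an earlier infigratinib study in cholangiocarcinoma, and from the planned maximum of 50 patients.

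- QTcF: no effect on ECG intervals had been noted, so the expected number is close to zero.
- Diarrhea: Grade 3-4 diarrhea is not listed among Grade 3-4 events at 5% or more. The implied ceiling is 0.05 × 50 = 2.5 patients with any Grade 3-4 diarrhea.
- Only those with a Grade 3 recurrence after reduction count. The documents give no recurrence share, so it is an assumption here. At 20% the ceiling is 0.20 × 2.5 = 0.5 patients, at 40% it is 1.0, and at 100% it is 2.5.

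**The case against.** The best reply is that the structure already answers the question. Most Table 6 rows say nothing about recurrence, so the sentence in Section 6.2.1 has a clear job as the default, and the two rows with their own instruction are the specific rule. The section ties dose modifications to the table. A site learns that it may re-treat after QTcF above 500 msec only from the row that also tells it what to do on recurrence, and in the diarrhea row the recurrence instruction directly follows the reduction. If the general sentence routinely turned these discontinuations into second reductions, the exceptional-continuation clause would have little to do for these rows. That clause also sends departures to one central decision-maker, and Section 8.3.2 requires monthly safety calls with all sites.

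Much of this stands. It makes divergent practice unlikely and supports one reading as the natural one. It remains an inference, because the general sentence is unqualified. The section also cannot be assumed to be fully harmonised: its text allows three reductions, while the closing note of Table 6 says that patients who need more than two are generally discontinued.

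A reader might extend the point to recurrent Grade 3 amylase or lipase elevation, where the table says that "despite dose reduction, drug should be held and continuation of therapy should be discussed with the medical monitor". The documents do not support counting this as an opposite instruction. Holding and discussing does not exclude a second reduction. That row also works from resolution to Grade 2 or lower, whereas the general rule begins from resolution to baseline or Grade 1.

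**Conclusion.** The inconsistency is real and confined to two rows: Grade 3 diarrhea recurring under optimised antidiarrheal treatment, and QTcF recurring above 500 msec after one reduction. What is missing is a statement of precedence.

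Its size is small: plausibly none or one of 50 patients. This assumes that the earlier study's toxicity profile carries over to this mixed-tumor population and that only a minority of Grade 3 diarrhea recurs after reduction.

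Two stronger conclusions are tempting. A reader might infer that the tolerability endpoints as a whole become site-dependent, but the expected count is too low for that. A reader might also infer a threat to the primary result. The sample size and the Cohort 1 decision rule (stop at 0 of 9 responders, promising at 4 or more of 30) do not depend on either text. The reason to act is that a safety stopping instruction should have one reading, and that the few affected patients should be handled and recorded alike at every site.

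**What to change.** Reconcile the general recurrence rule in Section 6.2.1 with the diarrhea and QTcF rows of Table 6. Add one sentence to Section 6.2.1 stating whether the general rule or the toxicity-specific row governs when a toxicity recurs at a reduced dose, and edit the other text to match. The sponsor's clinicians should decide which action applies to each toxicity; this review takes no position on that. The cost is one sentence and small table edits, which can go into an amendment. No statistical section needs to change.
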